12.2. Analyses of Safety Objectives

Safety will be summarized for maternal and infant subjects separately. Safety will be summarized overall and by treatment group for maternal and infant subjects based on percentages.

Tabulations of counts and proportions of the following safety parameters, by treatment group and overall, will be produced for maternal subjects:

- Solicited seven-day reactogenicity events by severity;
- Clinical laboratory safety abnormalities by severity;
- Caesarean, vaginal, and instrument-assisted vaginal modes of delivery;
- Pre-specified third-trimester pregnancy and delivery complications (i.e., stillbirth, placental abruption, preterm birth, preterm premature rupture of membranes, hypertensive disorders of pregnancy, third-trimester hemorrhage, and gestational diabetes), and labor and delivery complications (i.e., emergency Caesarean section, postpartum hemorrhage, chorioamnionitis, and maternal fever or infection); and
- Unsolicited adverse events through 180 days post-delivery by severity and relatedness (possibly, probably, or definitely), including SAEs, MAEs, and SNMCs.

Tabulations of counts and proportions of the following safety parameters, by treatment group and overall, will be produced for infant subjects:

- Congenital anomalies; respiratory failure other than RSV-associated hospitalization; neonatal death; infant death; sudden infant death syndrome; asphyxia; neonatal or hypoxic-ischemic encephalopathy; or other adverse events or complications of adverse events that necessitate hospitalization during the neonatal period and through the first year of life;
- All other unsolicited/unspecified adverse events by severity, relatedness, and seriousness, including respiratory events that test negative for RSV by RT-PCR.

Summary statistics will also be provided for infant length, weight, FOC, 1- and 5-minute APGAR scores, and responses to environmental and behavioral queries, through one year post-delivery overall, and by treatment group. Results of developmental testing will be summarized by treatment group, and percentages of infants in the developmental testing subset above normal, normal, at-risk at 6 or 12 months, and at-risk at both 6 and 12 months.

In addition, Chi-Square tests may be used to assess association between categorical variables, and logistic-regression models may be constructed to determine the predictors of RSV LRTI in infants. The candidate covariates for these models may include infant length, weight, FOC, APGAR score, and gestational age at birth.

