- Percentages of infants with RSV LRTI associated with EITHER hypoxemia (peripheral oxygen saturation [SpO_2] < 95% at sea level or < 92% at altitudes > 1800 meters) OR tachypnea (≥ 60 bpm for infants 0 to 59 days of age or ≥ 50 bpm for infants ≥ 60 days of age [WHO Handbook, Integrated Management of Childhood Illness criteria for tachypnea]) from delivery through 90, 120, 150, and 180 days of life. Data concerning documentation of RSV infection, LRTI symptoms and signs, hypoxemia and/or tachypnea may be obtained from the observations of the clinical site staff OR review and abstraction of medical records for infants undergoing hospitalization for a respiratory serious adverse event.
- Percentages of infants with RSV LRTI resulting in death from delivery through 90, 120, 150, and 180 days of life. Evidence of RSV infection and LRTI may be based on either or both of the observations of the clinical site staff using sponsor-supplied devices and diagnostic tests OR review and abstraction of medical records for infants undergoing hospitalization for a respiratory serious adverse event.
- Percentages of infants with RSV LRTI (all severities) from delivery through 90, 120, 150, and 180 days of life. Evidence of RSV infection and LRTI may be based on either or both of the observations of the clinical site staff using sponsor-supplied devices and diagnostic tests OR review and abstraction of medical records for infants undergoing hospitalization for a respiratory serious adverse event.
- Counts and incidence rates of infant healthcare interventions associated with wheezing through the first year of life.
- Percentages of maternal subjects with RSV-related respiratory illness as observed by the clinical study staff and detected by active and passive surveillance from vaccination through six months after delivery, overall and by pathogen(s).
- Percentages of infant subjects with all-cause LRTI, with or without tachypnea, hypoxemia, or severe hypoxemia, as detected by active and passive surveillance from vaccination through six months after delivery, overall and by pathogen(s).
- Percentages of infant and maternal subjects with non-RSV respiratory viruses, overall and by pathogen(s), through six months after delivery.

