- If the initial evaluation of the maternal or infant subject for an RSV-suspect illness is performed by a healthcare provider, not affiliated with the study (e.g., in an urgent care clinic, emergency room, or other outpatient clinic), he/she should notify the study staff of the maternal or infant subject's status as per the information provided on the Study Identification Card.
- Note: symptoms suggestive of an RSV-suspect illness reported during passive surveillance but after D+180 will be captured as AEs and not on the RSV Surveillance page.

Please refer to the **Study Operations Manual** for additional details regarding the procedures performed during the RSV Surveillance.

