best professional judgment to ensure that subjects receive prompt medical care appropriate to their clinical condition, if necessary either by referring the subject to their usual physician or medical care facility, or providing care if the investigator is the subject's primary physician or if the case is emergent. The collection of the study data to support the primary and secondary efficacy endpoints are key objectives of this trial, but when necessary, appropriate medical care should supersede this goal.

- Respiratory events captured as efficacy endpoints will NOT be recorded in the AE electronic case report form (eCRF) or AE eSource page, with the exception of those that fulfill the definition of an SAE. Full particulars of the SAE(s) will also be captured in the SAE report form.
- Respiratory events ongoing at the 6 months post-delivery visit (D+180) will be followed by study staff at weekly intervals until symptoms resolve or return to baseline.

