10.6 Safety Analyses

The primary variable for evaluation of the safety profile will be the number and percentage (95% CI) of maternal subjects with solicited and unsolicited AEs recorded post-vaccination and the number and percentage (95% CI) of infants with unsolicited AEs occurring since birth. Safety analyses will be performed using the Safety Population as defined in Section 10.1.

Safety will be summarized overall and by treatment group for maternal subjects based on Percentages of subjects with:

- Solicited seven day reactogenicity events by severity;
- Clinical laboratory safety abnormalities by severity;
- Caesarean, vaginal, and instrument-assisted vaginal modes of delivery;
- Specified third-trimester pregnancy complications (i.e., stillbirth, placental abruption, preterm birth, preterm premature rupture of membranes, hypertensive disorders of pregnancy, third-trimester hemorrhage, and gestational diabetes) and labor and delivery complications (i.e., emergency Caesarean section, postpartum hemorrhage, chorioamnionitis, and maternal fever or infection); and
- Unsolicited adverse events through 180 days post-delivery by severity and relatedness (possibly, probably, or definitely), including SAEs, MAEs, and SNMCs through 180 days post-delivery.

Clinical laboratory data summaries will include (by parameter and treatment group) toxicity grade shift summaries; absolute means and standard deviations with minima and maxima values, and tabulations of changes from baseline.

Safety analyses for infant subjects will be summarized overall and by treatment group, and will be based on percentages of infants with:

- Congenital anomalies; respiratory failure other than RSV-associated hospitalization; neonatal death; infant death; sudden infant death syndrome; asphyxia; neonatal or hypoxic-ischemic encephalopathy; or other adverse events or complications of adverse events that necessitate hospitalization during the neonatal period and through the first year of life;
- All other unsolicited/unspecified adverse events by severity, relatedness, and seriousness, including respiratory events that test negative for RSV by RT-PCR.

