- Percentages of infants with RSV LRTI associated with EITHER hypoxemia (peripheral oxygen saturation [SpO_2] $< 95\%$ at sea level or $< 92\%$ at altitudes > 1800 meters) OR tachypnea (≥ 60 bpm for infants 0 to 59 days of age or ≥ 50 bpm for infants ≥ 60 days of age [WHO Handbook, Integrated Management of Childhood Illness criteria for tachypnea]) from delivery through 90, 120, 150, and 180 days of life. Data concerning documentation of RSV infection, LRTI symptoms and signs, hypoxemia and/or tachypnea may be obtained from the observations of the clinical site staff OR review and abstraction of medical records for infants undergoing hospitalization for a respiratory serious adverse event.
- Percentages of infants with RSV LRTI resulting in death from delivery through 90, 120, 150, and 180 days of life. Evidence of RSV infection and LRTI may be based on either or both of the observations of the clinical site staff using sponsor-supplied devices and diagnostic tests OR review and abstraction of medical records for infants undergoing hospitalization for a respiratory serious adverse event.
- Percentages of infants with RSV LRTI (all severities) from delivery through 90, 120, 150, and 180 days of life. Evidence of RSV infection and LRTI may be based on either or both of the observations of the clinical site staff using sponsor-supplied devices and diagnostic tests OR review and abstraction of medical records for infants undergoing hospitalization for a respiratory serious adverse event.
- Counts and incidence rates of infant healthcare interventions associated with wheezing through the first year of life.
- Percentages of maternal subjects with RSV-related respiratory illness as observed by the clinical study staff and detected by active and passive surveillance from vaccination through six months after delivery, overall and by pathogen(s).

- Percentages of infant subjects with all-cause LRTI, with or without tachypnea, hypoxemia, or severe hypoxemia, as detected by active and passive surveillance from vaccination through six months after delivery, overall and by pathogen(s).
- Percentages of infant and maternal subjects with non-RSV respiratory viruses, overall and by pathogen(s), through six months after delivery.

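### The infant AE tables are said to include RSV-negative respiratory events, but on its plain reading the recording rule leaves non-serious RSV-negative LRTI through Day 180 without an AE record

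*SAP*

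**What the plan says.** SAP 12.2 lists what will be tabulated for infants by arm. After a set of named serious outcomes, the second item is "All other unsolicited/unspecified adverse events by severity, relatedness, and seriousness, including respiratory events that test negative for RSV by RT-PCR". Protocol 10.6 carries the same item with the same closing clause, "including respiratory events that test negative for RSV by RT-PCR". SAP 12.1 makes the number and percentage of infants with unsolicited AEs, with a 95% CI, part of the principal safety variable. SAP 12.4 presents the infant summaries to D+180 and/or D+364.

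Where an event is recorded is settled elsewhere. Protocol 6.2.5 says: "Respiratory events captured as efficacy endpoints will NOT be recorded in the AE electronic case report form (eCRF) or AE eSource page", and the only exemption is "with the exception of those that fulfill the definition of an SAE". Protocol 6.2.1 adds that suspect illness "reported during passive surveillance but after D+180 will be captured as AEs and not on the RSV Surveillance page". Protocol 6.1.2.10 repeats this for infants.

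The endpoint lists go beyond RSV. Protocol 3.2.5 includes "Percentages of infant subjects with all-cause LRTI, with or without tachypnea, hypoxemia, or severe hypoxemia, as detected by active and passive surveillance" through six months after delivery. SAP 4.2.3 repeats it under a heading that calls these exploratory efficacy endpoints. Both lists also include infants with non-RSV respiratory viruses.

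**The concern.** The safety section and the recording rule appear to point in opposite directions for one class of event: the non-serious respiratory illness that surveillance finds and that tests negative for RSV. If that illness counts as an efficacy endpoint, it stays on the RSV Surveillance page, yet the AE table is described as containing it.

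Two things are at stake. First, anyone reading the infant unsolicited-AE table would take it as a full count of RSV-negative respiratory illness by arm when it may hold mainly the serious cases. Second, a table running to D+364 would put two capture rules under one label, so infant respiratory AE rates before and after D+180 would not be comparable.

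The class is unlikely to be rare. Protocol 1.6.2 lists upper respiratory tract infection among the most commonly reported infant events in the Phase 2 trial. That trial enrolled only 50 women, and its figures are not restricted to non-serious or PCR-negative illness, so they supply no usable rate.

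**Working it through.** The question is one of data flow, so the check is to follow an RSV-negative infant illness from surveillance visit to recording page to table.

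**Is the illness an efficacy endpoint?** The objective behind the all-cause LRTI endpoint (protocol 2.3) speaks of the vaccine's efficacy in reducing it. SAP 10.5 gives non-RSV LRTI the same relative-risk analysis as the other exploratory efficacy endpoints. Protocol 6.2.3 treats the signs in Table 3 as the LRTI manifestations, and cough is one of them, so the class is broad.

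**Where does each case go?**

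- *Non-serious, before D+180, with an LRTI sign.* It is an exploratory efficacy endpoint, so 6.2.5 keeps it off the AE page. It is missing from the SAP 12.2 table.
- *Non-serious, before D+180, no LRTI sign but a non-RSV virus detected.* It is also on the exploratory endpoint list, and 6.2.5 reaches it if that listing counts as an efficacy endpoint, as the SAP heading implies.
- *Non-serious, before D+180, no LRTI sign and no virus.* It is not literally an endpoint. The documents do not clearly say where it is recorded.
- *Serious, at any time.* It is exempt from 6.2.5, so it has an SAE record and reaches the tables.
- *After D+180.* It is recorded as an AE. However, active surveillance largely ends at that visit (protocol 6.1.2.7), and the D+252 and D+364 visits list no respiratory sampling. These events are untested, not known to be RSV-negative.

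**Does anything bridge the gap?** The surveillance-visit procedures in protocol 6.2.3 include no AE severity grade or causality assessment. Protocol 8.3 and SAP 12.4 attach those to unsolicited AEs. SAP 16.6 has detailed rules for dating and merging surveillance episodes, but none carries an episode into the AE data. No section says that a negative central PCR result triggers an AE record.

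**Scale.** There is no plan figure to reproduce and no event rate to apply. As a unit conversion on the target enrolments in protocol Table 1 (live-born infants will be slightly fewer), each 10 percentage points of infants with such an illness is:

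- vaccine: 0.10 × 3,038 ≈ 304
- placebo: 0.10 × 1,562 ≈ 156

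This is a scale, not an estimate.

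**The case against.** The strongest reply is that the rules can be read together. Protocol 6.2.5 excludes only events captured as efficacy endpoints. The item just before it concerns the primary and secondary efficacy endpoints, all of which require RSV. Protocol 3.2.5 is headed as exploratory endpoints without the word efficacy, and the non-RSV virus objective is framed as epidemiology. On that reading RSV-confirmed endpoints stay off the AE page, RSV-negative illness is an ordinary AE, and the table is as described. Protocol 8.1 also requires all AEs to be collected at every scheduled visit, and protocol 8.3 grades them.

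This reading is possible, so 6.2.5 is ambiguous. But no text limits it to RSV-confirmed events, and the all-cause LRTI objective is worded in terms of efficacy. A site would also need the central PCR result before knowing which page to use, and no step for that is given. The general duty in 8.1 does not override a specific exception.

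Two further points stand. The D+180 sentence in 6.2.1 says what happens afterwards and does not itself bar earlier events; only 6.2.5 does, and it carries no date. The Study Operations Manual and the eCRF instructions are not among the documents and may contain the missing step.

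**Conclusion.** The inconsistency is real and should be corrected. On the plain reading, the infant AE table omits non-serious RSV-negative LRTI before D+180 that it claims to include, and infant respiratory AEs follow different capture rules on either side of D+180. This rests on taking all-cause LRTI as an efficacy endpoint for 6.2.5, as the protocol objective and the SAP heading indicate.

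A reader might infer more than the documents support:

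- *That these events are lost.* They are not. They remain on the surveillance page, and SAP 10.5 analyses non-RSV LRTI by arm and summarises infants with non-RSV viruses. What is missing is their place in the safety tabulation and any specified severity or relatedness grade.
- *That all early respiratory illness is excluded, or that RSV-negative events reappear after D+180.* Serious events are kept throughout, one group has no clear destination, and the later events are untested.
- *That the arm comparison is biased.* The rule is the same in both arms under blinding, so the loss should be similar. The harm is to completeness and absolute rates.
- *That the number missing can be stated.* It cannot, because the documents give no event rate.

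The primary analysis, Type I error and power are not affected.

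**What to change.** Reconcile SAP 12.2 and protocol 10.6 with protocol 6.2.5 and 6.2.1:

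- State in SAP 12.2 that the AE-page tables exclude non-serious respiratory illness captured by surveillance through D+180, label the tables accordingly, and align protocol 10.6.
- Add one by-arm row or table in the infant Safety Population, by treatment received, of RSV-negative and untested surveillance episodes through D+180, with n, % and 95% CI. Split it by seriousness but not by relatedness, since no causality assessment is specified for these episodes. Further splits by SpO2 or respiratory rate are optional.

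If the intent was that only RSV-confirmed endpoints stay off the AE page, say so in 6.2.5 and describe how a PCR-negative episode acquires an AE record with severity and causality.

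The recommended change costs SAP wording and one extra table from data already collected.
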